## 7.1. Critical Baseline Assessments

Efficacy assessments conducted at baseline are described in Section [7.2.2](#), tumour biomarker analysis are described in Section [7.6](#). Safety assessments conducted at baseline and during treatment are described in Section [7.4](#). Cardiovascular medical history/risk factors will be assessed at baseline.

### 7.1.1. Baseline Documentation of Intracranial Target and Non-Target Lesions

- All baseline lesion assessments must be performed 28 days prior to the first dose of study treatment.
- Measurable and non-measurable intracranial (i.e. brain parenchyma) lesions (refer to Section [7.3.1](#) for study definition of measurable intracranial lesions) up to a maximum of 5 lesions should be identified as target lesions, and recorded and measured at baseline. These lesions should be selected on the basis of their size (lesions with the longest diameter) and their suitability for accurate repeated measurements (by imaging techniques).

**Note:** Cystic lesions thought to represent cystic metastases should not be selected as target lesions when other suitable target lesions are available.

**Note:** Measurable intracranial lesions that have been previously irradiated and have not been shown to be progressing following irradiation should not be considered as target lesions.

- All other intracranial lesions should be identified as non-target and should also be recorded at baseline. Measurements of non-target lesions are not required, but the presence or absence of each should be noted throughout follow-up.

### 7.1.2. Baseline Documentation of Extracranial Target and Non-Target Lesions

- All baseline lesion assessments must be performed 28 days prior to the first dose of study treatment.
- Lymph nodes that have a short axis of <10mm are considered non-pathological and should not be recorded or followed.
- Pathological lymph nodes with <15mm and  $\geq 10$ mm short axis are considered non-measurable.
- Pathological lymph nodes with  $\geq 15$ mm short axis are considered measurable and can be selected as target lesions, however lymph nodes should not be selected as target lesions when other suitable target lesions are available.
- Measurable lesions up to a maximum of 2 lesions per organ and 5 lesions in total, representative of all involved extracranial organs, should be identified as target lesions, and recorded and measured at baseline. These lesions should be selected on the basis of their size (lesions with the longest diameter) and their suitability for

accurate repeated measurements (either by imaging techniques or clinically).

**Note:** Cystic lesions thought to represent cystic metastases should not be selected as target lesions when other suitable target lesions are available.

**Note:** Measurable extracranial lesions that have been previously irradiated and have not been shown to be progressing following irradiation should not be considered as target lesions.

- Lytic bone lesions or mixed lytic-blastic lesions, with identifiable soft tissue components, that can be evaluated by CT or MRI can be considered measurable. Bone scans, FDG-PET scans or X-rays are not considered adequate imaging techniques to measure bone lesions.
- All other lesions (or sites of disease, excluding the brain) should be identified as non-target and should also be recorded at baseline. Non-target lesions will be grouped by organ. Measurements of these lesions are not required, but the presence or absence of each should be noted throughout follow-up.

## 7.2. Efficacy

For this study, efficacy comprises intracranial, extracranial and overall response and disease control, duration of all responses, PFS, and OS. Intracranial, extracranial and overall response assessments conducted at baseline and during the study are described in Section 7.2. Intracranial, extracranial, and overall response will be assessed by RECIST 1.1 with modifications.

### 7.2.1. Efficacy Endpoints

[figure not shown]
The primary efficacy endpoint of this study is the intracranial response rate (IR) in BRAF V600E mutation positive subjects (Cohort A). The IR is defined as the percentage of subjects whose intracranial response is a confirmed Complete Response (CR) or Partial response (PR) assessed by investigator using modified RECIST 1.1 criteria.

#### 7.2.1.1. Secondary Endpoints

The following endpoints will be assessed as secondary endpoints in all cohorts (unless stated otherwise)

- IR in Cohort B, C and D
- Intracranial disease control (IDC)
- extracranial response rate (ERR)
- overall response rate (ORR)
- duration of intracranial, extracranial and overall response (DIR, DER and DOR respectively)
- progression-free survival (PFS)

- overall survival (OS) and long-term (particularly 3-year) OS
- Safety of dabrafenib and trametinib combination therapy

### 7.2.2. Efficacy Assessment

Disease progression and response evaluations for *intracranial* and *extracranial* disease will be determined according to the definitions established in the Response Evaluation Criteria in Solid Tumours (RECIST 1.1) [Eisenhauer, 2009]; Minor modifications will be applied to the assessment of intracranial lesions:

- **General:** target lesions should be representative of the subject's baseline tumour burden and should be selected based on their size (i.e. lesions with the longest diameter) and their suitability for accurate repeat assessment.
- **Intracranial lesions:** (the modifications to RECIST 1.1. impact the number and the minimal size of the target lesions selected at baseline) up to five lesions should be selected as target lesions; all brain lesions in excess of these five target lesions have to be regarded as non-target lesions. Measurable lesions are defined as those that can be accurately measured in at least one dimension with the longest diameter  $\geq 5$  mm when evaluated with contrast-enhanced MRI.

**Contrast-enhanced MRI is the only imaging modality accepted for the assessment of intracranial lesions.**

- **Extracranial lesions:** up to two lesions per organ representative of all involved organs should be selected as target lesions; the total number of target lesions should not exceed five and all lesions in excess of these five target lesions have to be regarded as non-target lesions.

See the Time and Events (Table 19) for the schedule of intracranial and overall efficacy assessments. Assessments must be performed on a calendar schedule and should not be affected by dose interruptions. For post baseline assessments, a window of  $\pm 3$  days is permitted to allow for flexible scheduling.

The following assessments are required at baseline:

- Contrast enhanced brain MRI
- CT for chest/abdomen/pelvis or MRI for abdomen/pelvis
- Clinical assessment for palpable and/or cutaneous lesions using callipers or photography.

As outlined in (Table 19) at specific post baseline assessment time points, repeat

evaluations of the target- and non-target lesions identified by the baseline MRI / CT scans and clinical assessments (calliper, photography) are required.

**Confirmation of intracranial, extracranial and overall CR and PR is required per protocol.** Confirmation assessments must be performed no less than 4 weeks after the criteria for response have initially been met and may be performed at the next protocol scheduled assessment. If a confirmation assessment is performed prior to the next protocol schedule assessment, the next protocol scheduled evaluation is still required (i.e., regularly scheduled study visit evaluations must occur at each protocol scheduled time point regardless of unscheduled assessments). If the criteria for a CR or PR are not confirmed, then stable disease (SD) can be considered the best response if it has been demonstrated for a minimum of 8 weeks.

#### 7.2.2.1. Assessment Guidelines

**For intracranial lesion assessments:**

- Contrast-enhanced MRI must be used throughout the study. Contrast-enhanced MRI is the only imaging modality accepted for the assessment of intracranial lesions.
- The technical specification of the MRI scanning sequences should be optimised for the evaluation of brain lesions which must be measured in the same anatomic plane by use of the same imaging examinations. Whenever possible the same scanner should be used. [Eisenhauer, 2009].
- As a modification to RECIST 1.1, target lesions as small as 5mm may be selected, however the scanning should be in accordance with RECIST 1.1: contiguous slices of maximum thickness corresponding to half the size of the lesion. [Eisenhauer, 2009] All measurements must be taken and recorded in millimetres (mm), using a ruler or callipers.
- Refer to Image Acquisition Guidelines (Brain MRI) for slice thickness requirements that should be performed in accordance with RECIST 1.1 criteria.

**For extracranial lesion assessments:**

- Contrast-enhanced CT (preferred) or MRI is recommended. 5 mm contiguous slices are recommended. The minimum size of a measurable extracranial baseline lesion should be twice the slice thickness, with a minimum lesion size of 10 mm. when the slice thickness is 5 mm. MRI is acceptable, but when used, the technical specification of the scanning sequences should be optimised for the evaluation of the type and site of disease and lesions must be measured in the same anatomic plane by use of the same imaging examinations. Whenever possible the same scanner should be used. [Eisenhauer, 2009].
- Clinical examination: Skin nodules or palpable lesions will only be considered measurable when they are superficial. In the case of skin lesions, documentation by colour photography (cameras will be provided by the sponsor from central vendor) is necessary. For both skin nodules and palpable lesions, size measurements using a ruler/calliper are required. [Eisenhauer, 2009].

- X-ray should not be used for target lesion measurements owing to poor lesion definition.
- Ultrasound is not a suitable modality of disease assessment. If new lesions are identified by ultrasound, confirmation by CT or MRI is required.
- Fluorodeoxyglucose (FDG)-PET is generally not suitable for ongoing assessments of disease. However FDG-PET can be useful in confirming new sites of disease where a positive FDG-PET scans correlates with the new site of disease present on CT/MRI or when a baseline FDG-PET was previously negative for the site of the new lesion. FDG-PET may also be used in lieu of a standard bone scan providing coverage allows interrogation of all likely sites of bone disease and FDG-PET is performed at all assessments.
- If PET/CT is performed then the CT component can only be used for standard response assessments if performed to diagnostic quality, which includes the required anatomical coverage and prescribed use of contrast. The method of assessment should be noted as CT on the CRF.

#### **7.2.2.2. Follow-Up Assessments for Subjects Permanently Discontinued from Study Treatment**

All subjects who permanently discontinue study treatment will have monthly skin assessments, survival follow up and new anti-cancer therapy (including radiotherapy and surgery follow up) through month 6 after treatment discontinuation. If they start new anti-cancer therapy or at the end of the 6 month follow up visit, they will be followed every 12 weeks for survival follow up and new anti-cancer therapy (including radiotherapy and surgery) until death or study completion. In addition, those subjects who permanently discontinue study treatment without progressive disease will have radiographic disease assessments performed on the same assessment schedule noted in the Time and Events ([Table 19](#)) every 8 weeks until Week 40 and then every 12 weeks thereafter until disease progression, start of new anti-cancer therapy or death.

#### **7.2.2.3. Assessment of Subject Completion**

If the last radiographic assessment for intracranial disease, extracranial disease or both was more than 8 weeks prior to discontinuation from study and progressive disease has not been documented, the appropriate disease assessment should be obtained at the time of study discontinuation.

### **7.3. Guidelines for Evaluation of Disease**

#### **7.3.1. Measurable and Non-Measurable Definitions for Intracranial Disease**

**Measurable intracranial lesion:** A lesion that can be accurately measured in at least one dimension with the longest diameter  $\geq 5$  mm when evaluated with contrast-enhanced MRI

**Non-measurable intracranial lesion:** All other lesions including lesions too small to be considered measurable (longest diameter  $< 5$  mm).

**Measurable intracranial disease:** The presence of at least one measurable lesion.

**Non-Measurable only intracranial disease:** The presence of only non-measurable lesions which would exclude the subject from participation in this study.

### **7.3.1.1. Measurable and Non-Measurable Definitions for Extracranial Disease**

**Measurable extracranial lesion:** A non nodal lesion that can be accurately measured in at least one dimension (longest dimension) of

- $\geq 10$  mm with MRI or CT with a recommended contiguous slice thickness of 5 mm. i.e. minimum size of measurable baseline lesion should be twice the slice thickness
- $\geq 10$  mm calliper/ruler measurement or medical photography.

Additionally lymph nodes can be considered pathologically enlarged and measurable if:

- $\geq 15$ mm in the short axis when assessed by CT or MRI (slice thickness recommended to be no more than 5mm). At baseline and follow-up, only the short axis will be measured [[Eisenhauer](#), 2009].

**Non-measurable extracranial lesion:** All other lesions including lesions too small to be considered measurable (longest diameter  $< 10$  mm or pathological lymph nodes with  $\geq 10$  mm and  $< 15$  mm short axis) as well as truly non-measurable lesions, which include: ascites, pleural or pericardial effusions, inflammatory breast disease, lymphangitic involvement of the skin or lung, abdominal masses/abdominal organomegaly identified by physical exam that is not measurable by reproducible imaging techniques [[Eisenhauer](#), 2009].

**Measurable extracranial disease:** The presence of at least one measurable lesion. Palpable lesions that are not measurable by radiologic or photographic evaluations may not be utilised as the only measurable lesion.

**Non-Measurable only extracranial disease:** The presence of only non-measurable lesions.

### **7.3.2. Response Criteria**

#### **7.3.2.1. Intracranial Response (IR) - Evaluation of Intracranial Target Lesions**

Definitions for assessment of response for *intracranial target* lesion(s) are as follows:

- Complete Response (CR): Disappearance of all target lesions.
- Partial Response (PR): At least a 30% decrease in the sum of the diameters of target lesions, taking as a reference, the baseline sum of the diameters (e.g. percent change from baseline).
- Stable Disease (SD): Neither sufficient shrinkage to qualify for PR nor sufficient increase to qualify for progressive disease.
- Progressive Disease (PD): At least a 20% increase in the sum of the diameters of target lesions, taking as a reference, the smallest sum of diameters recorded since the treatment started (e.g. percent change from nadir, where nadir is defined as the smallest sum of diameters recorded since treatment start). In addition, the sum must

have an absolute increase from nadir of 5mm.

- Not Evaluable (NE): Cannot be classified by one of the four preceding definitions.

**Note:**

- If an intracranial target lesion disappears and reappears at a subsequent time point it should continue to be measured. The response at the time when the lesion reappears will depend upon the status of the other lesions. For example, if the disease had reached a CR status then PD would be documented at the time of reappearance. However, if the response status was PR or SD, the diameter of the reappearing lesion should be added to the remaining diameters and response determined based on percent change from baseline and percent change from nadir.

**7.3.2.2. Intracranial Response (IR) - Evaluation of Intracranial Non-Target Lesions**

Definitions for assessment of response for intracranial non-target lesions are as follows:

- Complete Response (CR): The disappearance of all non-target lesions.
- Non-CR/Non-PD: The persistence of 1 or more non-target lesion(s) identified as a site of disease.
- Progressive Disease (PD): Unequivocal progression of existing non-target lesions.
- Not Applicable (NA): No intracranial non-target lesions at baseline.
- Not Evaluable (NE): Cannot be classified by one of the four preceding definitions.

**Note:**

- Intracranial non-target lesions, which are not assessed at a particular timepoint based on the assessment schedule, should be excluded from the response determination (e.g. non-target response does not have to be "Not Evaluable").

**7.3.2.3. Extracranial Response (ER) - Evaluation of Extracranial Target Lesions**

Definitions for assessment of response for *extracranial target* lesion(s) are as follows:

- Complete Response (CR): Disappearance of all target lesions.
- Partial Response (PR): At least a 30% decrease in the sum of the diameters of target lesions, taking as a reference, the baseline sum of the diameters (e.g. percent change from baseline).
- Stable Disease (SD): Neither sufficient shrinkage to qualify for PR nor sufficient increase to qualify for progressive disease.
- Progressive Disease (PD): At least a 20% increase in the sum of the diameters of target lesions, taking as a reference, the smallest sum of diameters recorded since the treatment started (e.g. percent change from nadir, where nadir is defined as the smallest sum of diameters recorded since treatment start). In addition, the sum must

have an absolute increase from nadir of 5mm.

- Not Evaluable (NE): Cannot be classified by one of the four preceding definitions.

**Note:**

- If an extracranial target lesion disappears and reappears at a subsequent time point it should continue to be measured. The response at the time when the lesion reappears will depend upon the status of the other lesions. For example, if the disease had reached a CR status then PD would be documented at the time of reappearance. However, if the response status was PR or SD, the diameter of the reappearing lesion should be added to the remaining diameters and response determined based on percent change from baseline and percent change from nadir.

**7.3.2.4. Extracranial Response (ER) - Evaluation of Extracranial Non-Target Lesions**

Definitions for assessment of response for extracranial non-target lesions are as follows:

- Complete Response (CR): The disappearance of all non-target lesions.
- Non-CR/Non-PD: The persistence of 1 or more non-target lesion(s) identified as a site of disease.
- Progressive Disease (PD): Unequivocal progression of existing non-target lesions.
- Not Applicable (NA): No extracranial non-target lesions at baseline.
- Not Evaluable (NE): Cannot be classified by one of the four preceding definitions.

**Note:**

- Extracranial non-target lesions which are not assessed at a particular timepoint based on the assessment schedule should be excluded from the response determination (that is., the non-target response does not have to be "Not Evaluable" if the non-target lesions were not scheduled for assessment at a particular timepoint).

**7.3.2.5. Overall Response - Evaluation of Target Lesions**

Overall target lesion response is based on all (that is, intracranial and extracranial) target lesions, up to 10 total. The sum of longest diameters of all target lesions will be used to determine overall response. Definitions for assessment of response for target lesion(s) based on modified RECIST 1.1 are as follows:

- Complete Response (CR): Disappearance of all target lesions. Any pathological lymph nodes must be <10mm in the short axis.
- Partial Response (PR): At least a 30% decrease in the sum of the diameters of target lesions, taking as a reference, the baseline sum of the diameters (e.g. percent change from baseline).
- Stable Disease (SD): Neither sufficient shrinkage to qualify for PR nor sufficient increase to qualify for progressive disease.

- **Progressive Disease (PD):** At least a 20% increase in the sum of the diameters of target lesions, taking as a reference, the smallest sum of diameters recorded since the treatment started (e.g. percent change from nadir, where nadir is defined as the smallest sum of diameters recorded since treatment start). In addition, the sum must have an absolute increase from nadir of 5mm.
- **Not Applicable (NA):** No extracranial target lesions at baseline.
- **Not Evaluable (NE):** Cannot be classified by one of the five preceding definitions.

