**7.3.2.6. Overall Response - Evaluation of Non-Target Lesions**

Overall non-target lesion response is based on all (that is, intracranial and extracranial) non-target lesions. Definitions for assessment of response for non-target lesions are as follows:

- **Complete Response (CR):** The disappearance of all non-target lesions. All lymph nodes identified as a site of disease at baseline must be non-pathological (e.g. <10 mm short axis).
- **Non-CR/Non-PD:** The persistence of 1 or more non-target lesion(s) or lymph nodes identified as a site of disease at baseline  $\geq 10$  mm short axis.
- **Progressive Disease (PD):** Unequivocal progression of existing non-target lesions.

- Not Applicable (NA): No intracranial or extracranial non-target lesions at baseline.
- Not Evaluable (NE): Cannot be classified by one of the five preceding definitions.

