**7.3.2.10. Evaluation of Overall Response**

[Table 22](#) presents the overall response at an individual time point for all possible

combinations of tumour responses in all intracranial and extracranial target and non-target lesions with or without the appearance of new lesions.

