**Table 22 Evaluation of Overall Response**

Target Lesions	Non-Target Lesions	New Lesions	Overall Response
CR	C	No	CR
CR	Non-CR/Non-PD or	No	PR
PR	Non-PD or NA or	No	PR
SD	Non-PD or NA or	No	SD
NE	Non-PD or NA or	No	NE
PD	A	Yes or No	PD
Any	P	Yes or No	PD
Any	A	Yes	PD

CR=complete response, PR = partial response, SD=stable disease, PD=progressive disease, NA= Not applicable, and NE=Not Evaluable

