## Overall Response (OR) in Cohorts A, B, C, and D

The overall response rate (ORR) is defined as the percentage of subjects achieving a confirmed overall CR or PR from the start of treatment until disease progression or the start of new anti-cancer therapy. This will be based on investigator-assessed best overall response.

Stable disease requires meeting the SD criteria for both intracranial and extracranial disease at least once after the first dose of study treatment at a minimum interval of 8 weeks. To be assigned a status of overall PR or CR, a confirmatory disease assessment for both intracranial and extracranial disease should be performed not less than 4 weeks after the criteria for response are first met.

The Independent Reviewer-assessed best overall response will also be summarized.

Subjects with Not Evaluable (NE) or missing overall response will be treated as non-responders; i.e., they will be included in the denominator when calculating the percentage.

The exact 95% CI for the overall response rate will be calculated.

All data relating to overall response from the investigator and, if done, the independent reviewer will be listed, including lesion measurements, response assessments and best response.

A plot of the maximum percent tumor reduction in overall target lesions from baseline will be provided. The plot will be color-coded for best overall response. The subject number will be indicated on the plot.

Overall response will be determined using both extracranial and intracranial target, non-target, and new lesions, using the criteria specified in the protocol. Overall target lesion response is based on all (that is, intracranial and extracranial) target lesions, up to 10 total. The sum of longest diameters of all intracranial and extracranial target lesions will be used to determine overall response. Unequivocal new intracranial or extracranial (or both) lesions, or unequivocal intracranial or extracranial (or both) non-target lesion progression indicate overall progression. Target, non-target, and new lesion responses are combined as for intracranial and extracranial response to determine response at each disease assessment and best overall response.

- Complete Response (CR): Disappearance of all intracranial and extracranial target lesions. Any pathological lymph nodes must be <10mm in the short axis.

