- Partial Response (PR): At least a 30% decrease in the sum of the diameters of intracranial and extracranial target lesions, taking as a reference, the baseline sum of the intracranial and extracranial diameters (e.g. percent change from baseline).
- Stable Disease (SD): Neither sufficient shrinkage to qualify for PR nor sufficient increase to qualify for progressive disease.
- Progressive Disease (PD): At least a 20% increase in the sum of the diameters of intracranial and extracranial target lesions, taking as a reference, the smallest sum of intracranial and extracranial diameters recorded since the treatment started (e.g.,

percent change from nadir, where nadir is defined as the smallest sum of diameters recorded since treatment start). In addition, the sum must have an absolute increase from nadir of 5mm.

- Not Evaluable (NE): Cannot be classified by one of the five preceding definitions.

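### Protocol 7.3.2.5 makes overall target-lesion response both the combined sum and Not Applicable for subjects whose only target lesions are in the brain

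*Protocol*

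**What the plan says.** Protocol 7.3.2.5 opens with the rule "Overall target lesion response is based on all (that is, intracranial and extracranial) target lesions, up to 10 total", and the summed diameters of those targets decide the response. It then defines CR, PR, SD and PD on that sum and adds a fifth category, NA, defined as "No extracranial target lesions at baseline".

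Protocol 7.3.2.10 introduces Table 22 as covering every possible case of "combinations of tumour responses in all intracranial and extracranial target and non-target lesions". The target column of Table 22 holds CR, PR, SD, NE, PD and Any. NA does not appear there.

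SAP 11.2 also uses the sum over both compartments for overall response. It lists CR, PR, SD, PD and NE, with no NA, but refers back to the protocol's criteria. Its NE line reads "Cannot be classified by one of the five preceding definitions", although only four definitions come before it.

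Protocol 7.3.2.11 has the sponsor program best overall response from the investigator's overall response at each time point.

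**The concern.** One section gives two answers for the same subject. A subject with brain targets and no extracranial target has a well-defined sum of diameters, so CR, PR, SD or PD can be assigned. The same subject also fits the NA line, and nothing says which takes precedence. NA is a baseline status, so a site that applied it would do so at every visit.

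Four secondary endpoints depend on overall response or overall progression: ORR, overall disease control (ODC), duration of overall response (DOR) and PFS, in all four cohorts. Best overall response is built from what the site recorded, so a site's NA could pass into the analysis even though the SAP's own list omits it. The primary endpoint, intracranial response in Cohort A, uses intracranial lesions only and is not touched.

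**Working it through.** The plan gives no figure on this point to reproduce. The check is a comparison of text, followed by an illustration of size.

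**1. Who is affected.** Inclusion criterion 6 (Protocol 4.1.2) requires a measurable brain lesion that is untreated or progressing. Protocol 7.3.1 rules out non-measurable-only intracranial disease. Protocol 7.3.1.1 describes non-measurable-only extracranial disease without excluding it, and no visible criterion requires an extracranial target. So every eligible subject has a brain lesion that can serve as a target, and some may have no other target. The NA line as worded can only catch the latter.

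**2. The category lists side by side.**

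| List | NA category | Definitions before NE | NE line counts |
|---|---|---|---|
| Protocol 7.3.2.3, extracranial targets | none | 4 | four |
| Protocol 7.3.2.5, overall targets | "No extracranial target lesions at baseline" | 5 | five |
| Protocol 7.3.2.6, overall non-targets | "No intracranial or extracranial non-target lesions at baseline" | 4 | five |
| SAP 11.2, overall response | none | 4 | five |

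The overall non-target list names both compartments; the overall target list names one. The extracranial target list, where the wording would fit, has no NA. The line looks misplaced or half-written.

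**3. Table 22 with a target status of NA.** Only the two Any rows can match, and both return PD, from non-target progression or from a new lesion. No row returns CR, PR or SD, and none returns PD from target growth.

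**4. One record.** Take brain targets only, stable or absent non-target lesions, and no new lesions. The brain sum is down 50% at Weeks 8 and 16, then rises 40% from nadir with an absolute rise of at least 5 mm.

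- On the PR and PD definitions of 7.3.2.5 and the sum rule of SAP 11.2: overall PR, confirmed 8 weeks later, then overall PD and a PFS event.
- On the NA line: Table 22 gives no result at any of these visits.

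**5. PFS under the NA line.** SAP 11.2 counts an assessment as adequate only if the response is CR, PR or SD. A subject coded NA throughout has none. If that subject remains event-free, the only fallback date in the SAP's rules is the first dose.

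**6. Size for ORR.** Let f be the share coded NA and p the true ORR, assumed equal in subjects with and without extracranial targets. The documents do not give f; 5%, 10% and 20% are assumed. If NA counts as non-response, reported ORR = p × (1 − f). With p = 0.50:

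- f = 0.05: 0.50 × 0.95 = 47.5%
- f = 0.10: 0.50 × 0.90 = 45%
- f = 0.20: 0.50 × 0.80 = 40%

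In whole subjects, with n = 75 and 38 true responders (50.7%), and exact 95% intervals:

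| f | Coded NA | Responders left | NA kept as non-responders | NA dropped |
|---|---|---|---|---|
| 5% | 4 | 36 | 36/75 = 48.0% (36.3 to 59.8) | 36/71 = 50.7% (38.6 to 62.8) |
| 10% | 8 | 34 | 34/75 = 45.3% (33.8 to 57.3) | 34/67 = 50.7% (38.2 to 63.2) |
| 20% | 15 | 30 | 30/75 = 40.0% (28.9 to 52.0) | 30/60 = 50.0% (36.8 to 63.2) |

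Neither document says which column applies. Protocol 9.3.5.1.1 (Secondary Analyses) and SAP 11.2 make NE and missing responses non-responders and do not mention NA. SAP 9.1 says that a Not applicable answer is not missing data.

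**The case against.** The best defence is that this is one stray line and that the rest of the plan points to the right result. The opening of 7.3.2.5, its PR and PD definitions and SAP 11.2 all work from the combined sum. The SAP list has no NA, and footnote 1 to SAP Table 2 dates progression from growth in the measured lesions. Whether the case report form offered NA as an overall response cannot be seen, and derivation details sit in separate dataset specifications. Much of this stands. It does not settle the matter, because SAP 11.2 defers to the protocol's criteria and the analysis starts from the investigator's recorded response.

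A reader might also infer four stronger things that the documents do not support:

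- *That these subjects cannot be overall responders.* A 30% fall in the brain sum meets the PR definition in the same section, and NA is given no precedence over it.
- *That NA means missing, hence non-responder.* SAP 9.1 says the opposite about missingness, and no rule covers an overall NA.
- *That they cannot meet the SAP's confirmation rule,* "To be assigned a status of overall PR or CR, a confirmatory disease assessment for both intracranial and extracranial disease should be performed". This asks that both compartments be assessed, not that both respond. Body imaging is scheduled at the same visits as brain imaging, and a subject without extracranial targets can have it. Such a subject may also have extracranial non-target disease to assess.
- *That the miscount in the SAP's NE line shows NA is still in force there.* Protocol 7.3.2.6 miscounts in the same way, so this is weak evidence.

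**Conclusion.** Protocol 7.3.2.5 is wrong as written. It contradicts its own opening rule, and Table 22 cannot process the category it creates. For subjects whose only targets are in the brain, overall classification is contradictory; the text does not definitely exclude them. If sites followed the NA line, these subjects would lose overall CR, PR and SD and target-based overall PD, and would have no adequate assessment for PFS. Overall PD from a new lesion or non-target progression would remain possible.

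The size depends on an unknown share. At an assumed 5% to 20% coded NA and kept as non-responders, a true ORR of 50% would be reported as 47.5% to 40%. If they left the denominator, ORR would stay near 50%, on 71 to 60 of 75 subjects, with a wider interval. Both figures assume the same response rate with and without extracranial targets. The affected endpoints are secondary and carry no hypothesis test.

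**What to change.** - **Protocol 7.3.2.5.** Delete the NA line, or reword it so that it requires no target lesion in either compartment. Add a sentence: with no extracranial targets, overall target response is determined from the intracranial sum alone.
- **Counts.** If the line is deleted, the NE count in 7.3.2.5 becomes four; if it is reworded, five stays right. In SAP 11.2 the count should be four, to match its list. The count in 7.3.2.6 can be corrected at the same time.
- **If NA is instead moved to 7.3.2.3,** where the NE line now reads "Cannot be classified by one of the four preceding definitions", change that count to five and the count in 7.3.2.5 to four. Add the matching row to Table 21 and state how NA enters the extracranial response denominator.
- **SAP 11.2.** State how any overall NA already recorded is handled in the ORR denominator.

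The cost is wording only, with no new data. The target-lesion and tumour-response listings already planned in SAP 14.1 (22.0040 and 22.0070) can show how many subjects had no extracranial target and whether an overall NA was recorded for any of them. That would replace the assumed share.
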